#### 3. STUDY POPULATION

#### 3.1. Inclusion Criteria:

**3.1.1.** Adolescent (12 to 18 years) and adult (19 to 60 years) patients who have relapsed or refractory T-cell lymphoblastic leukemia (T-ALL) or T-Cell lymphoblastic lymphoma (T-LBL) according to 2017 WHO classification [29] and NCCN v1 2021 [30]:

Patients must have  $\geq 5\%$  blasts in the bone marrow as assessed by morphology on standard bone marrow biopsy and aspirate or less than 5% blasts in the bone marrow in presence of extramedullary relapse, excluding isolated central nervous system (CNS) relapse. However, if an adequate bone marrow sample cannot be obtained, patients may be enrolled if there is unequivocal evidence of leukemia with  $\geq 5\%$  blasts in the peripheral blood.

- **3.1.2.** Patients are eligible independently of Notch pathway activation in the leukemic blasts: however, a fresh marrow/blood sample must be obtained before starting the study treatment to classify the patients as being either Notch positive or negative.
- **3.1.3.** Leukemic blasts must express of at least 2 of the following immune phenotyping: CD1a, CD2, CD3, CD4, CD5, CD7, CD8, CD34, TCR $\alpha$ B, TCR $\gamma$ S, cyCD3
- **3.1.4.** Patients have adequate performance status (ECOG ≤2) for patients ≥16 years old, Lansky score >50 for patients <16 years old.
- **3.1.5.** Patients must be 12 to 60 years of age inclusive when signing the informed consent. For patients < 18 years of age, parent or legally authorized representative (LAR) should be willing and able to give informed consent. Non-English speaking patients are eligible for whom consent process will follow institutional guidelines.
- **3.1.6.** Patients with CNS disease are eligible.
- **3.1.7.** Patients must have adequate organ function and laboratory results (obtained within 14 days of enrollment):
  - **3.1.7.1.** Direct bilirubin  $\leq 2$  x upper limit of normal (ULN).
  - **3.1.7.2.** Serum creatinine  $\leq$  1.5 x ULN; or if serum creatinine > 1.5 x ULN, then serum creatinine clearance (CrCl)  $\geq$  50 mL/min (estimated by Cockcroft-Gault formula).
  - **3.1.7.3.** Alanine aminotransferase (ALT) and/or aspartate aminotransferase (AST)  $\leq$ 3 x ULN;  $\leq$ 5 x ULN in case of suspected leukemic liver involvement

Page | 9 04/25/2024

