# 6.1.1. Dose modification for renal toxicity (Table 7).

If serum creatinine  $\geq 2$  x ULN has been demonstrated, this parameter must be repeated at least twice a week until resolution to  $\leq$  CTCAE grade 1, to allow for initiation of re-treatment and then at least weekly until either resolution or until stabilisation.

If proteinuria or haematuria  $\geq$  CTCAE grade 2 or serum creatinine  $\geq$  2.0 x ULN has been demonstrated, a 24-hour urine collection must be obtained for total protein and total creatinine and must be repeated at least weekly until either resolution to baseline value to allow for initiation of re-treatment, or until stabilisation. Whenever a measured CrCl is obtained, a serum creatinine value should be obtained within  $\leq$  72 hours of the urine collection.

Table 7: Dose modifications for renal toxicities

Dose Modifications for CB-103		
Worst Toxicity  CTCAE Grade unless otherwise specified (Value)  At any time during a cycle of CB-103 (including intended day of dosing)		
Serum creatinine		
(< 2 x ULN)	Maintain dose level	
(2 - 3 x ULN)	Omit dose administration until resolved to ≤ Grade 1, • If resolved in ≤ 7 days, then maintain dose level • If resolved in > 7 days, then ↓ 1 dose level	
Grade 3 (> 3.0 - 6.0 x ULN) & Grade 4 (> 6.0 x ULN)	Omit dose administration and discontinue patient from study treatment	

Abbreviations: AE, adverse event; CTCAE, Common Terminology Criteria for Adverse Events; LLN, lower limit of normal; ULN, upper limit of normal. Grading according to NCI-CTCAE v.5.0 guideline.

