# 6.1.2. Dose modification for liver toxicity (Table 8).

If bilirubin or AST/ALT > CTCAE grade 2 has been demonstrated, these parameters must be repeated at least twice a week until resolution to < CTCAE grade 1, to allow for initiation of re-treatment and then at least weekly until either resolution or until stabilisation.

Page | 20 04/25/2024

Patients with total bilirubin > ULN (any duration) should have fractionation of bilirubin into total/direct or indirect/direct components and any additional work-up as clinically indicated by these results. Follow-up of hyperbilirubinaemia should proceed as per the guidelines above, irrespective of the results of fractionation.

**Table 8:** Dose modifications for hepatic toxicities

Dose Modifications for CB-103			
Worst Toxicity CTCAE Grade unless otherwise specified (Value)	At any time during a cycle of CB-103 (including intended day of dosing)		
Bilirubin			
Grade 1 (< 1.5 x ULN)	Maintain dose level		
Grade 2 (1.5 - 3 x ULN)	Omit dose administration until resolved to ≤ Grade 1,  • If resolved in ≤ 7 days, then maintain dose level  • If resolved in > 7 days, then ↓ 1 dose level		
Grade 3 (> 3–0 - 10.0 x ULN)	Omit dose administration until resolved to $\leqslant$ Grade 1, then $\downarrow$ 1 dose level		
Grade 4 (> 10.0 x ULN)	Omit dose administration and discontinue patient from study treatment		
AST or ALT			
Grade 1 (> ULN - 3.0 x ULN) & Grade 2 (>3.0 - 5.0 x ULN) without increase in total bilirubin >2 x ULN	Maintain dose level		
Grade 3 (> 5.0 - 20.0 x ULN) without increase in total	Omit dose administration until resolved to ≤ Grade 1 (or ≤ Grade 2 in case of liver metastasis), then		
bilirubin >2 x ULN	• If resolved in $\leqslant$ 7 days, then maintain dose level		
	• If resolved in > 7 days, then ↓ 1 dose level		
Grade 4 (> 20.0 x ULN) without increase in total bilirubin >2 x ULN	Omit dose administration until resolved to ≤ Grade 1, then ↓ 1 dose level		

Abbreviations: AE, adverse event; ALT, alanine aminotransferase; ANC, absolute neutrophil count; AST, aspartate aminotransferase; CTCAE, Common Terminology Criteria for Adverse Events; LLN, lower limit of normal; PLT, platelets; ULN, upper limit of normal. Grading according to NCI-CTCAE v.5.0 guideline.

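### Entry limits in 3.1.7 admit some patients whose creatinine or bilirubin already falls in a CB-103 hold or stop row of Tables 7 and 8 (minor inconsistency)

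*Combined protocol and SAP*

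**What the plan says.** **Entry (section 3.1.7).** Creatinine may be up to 1.5 x ULN, "or if serum creatinine > 1.5 x ULN, then serum creatinine clearance (CrCl" must be at least 50 mL/min by Cockcroft-Gault. That branch has no upper creatinine limit. For bilirubin, only the direct fraction is limited, to 2 x ULN. No limit on total bilirubin is given.

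**Dosing (section 6.1).** Tables 7 and 8 apply "At any time during a cycle of CB-103 (including intended day of dosing", and section 6.1 tells the investigator to follow them. For creatinine 2-3 x ULN, Table 7 says "Omit dose administration until resolved to ≤ Grade 1". For "Grade 3 (> 3.0 - 6.0 x ULN) & Grade 4 (> 6.0 x ULN" it ends study treatment. Table 8 imposes the same hold for bilirubin in its row "Grade 2 (1.5 - 3 x ULN", holds Grade 3 and then reduces the dose, and stops at Grade 4.

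**Contrast.** Table 9 (visual symptoms) and Table 11 (diarrhoea) accept return to baseline as an alternative. The creatinine and bilirubin rows do not.

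**The concern.** A stable laboratory value can pass the entry criterion and, at the same level, fall in a row that bars the investigational drug on the first dosing day. For creatinine above 3 x ULN the two rules are opposite: the patient may enrol, and Table 7 then ends treatment. In the hold rows, a patient whose value never falls to Grade 1 or below has no printed route to a first dose of CB-103.

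At stake is whether an eligible patient is dosed, at what level, and whether that patient can count toward the response endpoint in a trial of at most 30. A clear instruction should not depend on an investigator deciding which of two sections prevails.

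**Working it through.** The plan states no figure on this point, so the check compares the limits and asks whether the overlap can occur in practice.

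**1. Creatinine.** Inputs from the plan: minimum CrCl 50 mL/min, Cockcroft-Gault, ages 12-60 (section 3.1), and Table 7 thresholds of 2 and 3 x ULN. The plan gives no creatinine ULN. I assume 1.0-1.2 mg/dL for adults and 0.8-1.2 for adolescents.

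CrCl = (140 - age) x weight x f / (72 x creatinine), with f = 1 for men and 0.85 for women. Setting creatinine = k x ULN and solving for the lowest weight at which the patient is still eligible:

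weight = 72 x CrCl x k x ULN / ((140 - age) x f)

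Example: man, age 20, CrCl 50, k = 2, ULN 1.0: 72 x 50 x 2 x 1.0 / 120 = 60.0 kg. With ULN 1.2 it is 72.0 kg.

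| Age | Men, 2 x ULN | Women, 2 x ULN | Men, 3 x ULN |
|---|---|---|---|
| 15 | 46-69 kg | 54-81 kg | 69-104 kg |
| 20 | 60-72 kg | 71-85 kg | 90-108 kg |
| 40 | 72-86 kg | 85-102 kg | 108-130 kg |
| 60 | 90-108 kg | 106-127 kg | 135-162 kg |

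The ranges span the assumed ULN. With a male ULN as high as 1.4, the age-20 figure at 2 x ULN rises to 72 x 50 x 2 x 1.4 / 120 = 84 kg. At CrCl 60 every weight is 20% higher. Below these weights there is no conflict. A 40-year-old, 70 kg man at CrCl 50 has creatinine of 100 x 70 / 3,600 = 1.94 mg/dL, or 1.6-1.9 x ULN, which is under the hold threshold.

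So the hold row is reachable at ordinary weights in younger patients. The stop row needs a heavier one. For example, a 20-year-old, 110 kg man with creatinine 3.62 mg/dL (just over 3 x an ULN of 1.2) has CrCl 120 x 110 / (72 x 3.62) = 50.6 and is eligible.

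**2. Bilirubin.** The Table 8 rows do not name the fraction. Section 6.1.2 suggests total: "Patients with total bilirubin > ULN (any duration) should have fractionation of bilirubin into total/direct or indirect/direct components", with follow-up the same whatever fractionation shows. Section 8.9.3 measures direct bilirubin only when total is raised. The overlap exists under either reading:

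- Total: any value of 1.5 x ULN or more is eligible if direct is at most 2 x ULN.
- Direct: values of 1.5-2 x ULN are eligible and in the hold row.

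**3. AST/ALT for comparison.** Entry allows up to 5 x ULN with suspected liver involvement, and Table 8 maintains dose up to 5 x ULN if total bilirubin is not above 2 x ULN. There the limits match.

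**4. Conditional consequence for dose.** If the cycle clock starts on Day 1 with CB-103 on hold, and the hold is long, then "If resolved in > 7 days, then ↓ 1 dose level" makes the first dose 400 mg BID (800 mg/day). Planned cycle 1 dosing days are 1-5, 8-12, 15-19 and 22-26, so the planned dose is 20 x 1,000 = 20,000 mg. Section 9 requires more than 50% of the CB-103 dose for response evaluability, without giving the denominator.

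- One-cycle denominator, first dose Day 10: 13 x 800 = 10,400 mg (52%). Day 11: 12 x 800 = 9,600 mg (48%, not evaluable).
- Two-cycle denominator (40,000 mg), first dose Day 19: 26 x 800 = 20,800 mg (52%). Day 22, the next dosing day: 25 x 800 = 20,000 mg (50.0%, not evaluable).

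**The case against.** **These are toxicity tables.** Rows are indexed by worst toxicity, and the surrounding text speaks of re-treatment. Section 9.2.2.1 counts a pre-existing condition as an adverse event only if it worsens. Section 4.3 leaves dose changes to the treating physician or principal investigator. An investigator could fairly treat a stable baseline value as outside the tables. This stands as a plausible reading. But 9.2.2.1 defines adverse events rather than dosing, and no dosing text exempts a baseline value. How CTCAE v5.0, which the tables cite, handles an abnormal baseline cannot be checked from these documents.

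**Other text may cover it.** Section 6.1.1 does mention "resolution to baseline value to allow for initiation of re-treatment", but for the repeated 24-hour urine collection; its sentence on serum creatinine still requires Grade 1 or below. Section 3.2.16 lets the investigator exclude a patient with a risky laboratory abnormality, and 3.2.8 excludes active severe liver disease. Neither says how to dose a patient who is enrolled.

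**A strict dosing-day hold can coexist with a looser entry limit**, and leaving out a baseline alternative may be deliberate: section 2.3.2 reports two related liver-injury SAEs with CB-103. That is a good reason not to assume that a baseline clause is the right repair. It does not explain admitting a patient whom Table 7 would discontinue at once.

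**Stronger readings that a reader might infer.** Because section 6.1 makes the two drugs' modifications independent, one might conclude that such patients will start venetoclax alone and lose evaluability. The documents do not establish this. Section 5.2.3 asks that abnormal chemistry, creatinine included, be corrected before venetoclax, so an uncorrected creatinine would hold both drugs. Sections 4.1 and 4.2.1 define the cycle by both drugs, so Day 1 could simply be deferred. In that case the percentages in step 4 do not arise. Nor is there a basis for inferring inconsistent handling across sites, since section 12 describes a single institution.

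**Conclusion.** The inconsistency is real but minor. Entry and dosing limits overlap on the printed numbers, for creatinine from 2 x ULN and for bilirubin from 1.5 x ULN. The clearest case is creatinine above 3 x ULN with CrCl of at least 50 mL/min: eligible and, read literally, due for discontinuation on the first dosing day.

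The creatinine weights rest on the assumed ULN. The bilirubin overlap needs no such assumption. The documents give no frequency, and few patients are likely to be affected. A venetoclax-only start, a reduced first dose and loss of evaluability are possible outcomes of a literal reading, not established ones. The sample size, stopping boundaries and operating characteristics in section 12 are unchanged.

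**What to change.** 1. In the CrCl branch of 3.1.7.2, cap entry creatinine at 3 x ULN, and add a total bilirubin entry limit of 3 x ULN to 3.1.7. No patient eligible on those values then starts in a Grade 3 or discontinue row for creatinine or bilirubin. This step is worth making on its own.
2. State in Table 8 which bilirubin fraction the rows use.
3. For creatinine 2-3 x ULN and bilirubin 1.5-3 x ULN, align the two rules in one of two ways. Either add a baseline alternative for a documented stable entry value, in the table rows and in the matching text of 6.1.1 and 6.1.2, or lower the entry limits to the hold thresholds. This is a clinical choice, to be made in view of the two liver-injury SAEs in section 2.3.2.

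A baseline clause without step 1 would leave the creatinine stop row in conflict.

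**Cost.** A wording amendment to 3.1.7, 6.1.1, 6.1.2 and Tables 7 and 8. No new tests are needed, because creatinine and total bilirubin are already in the section 8.9.3 panel. A very small number of patients would be excluded or, under a baseline clause, dosed at a raised stable value that 3.1.7 already accepts.

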#### 3.2. Exclusion Criteria

Patients who meet any of the following criteria will be excluded from participation in the study:

- 3.2.1. Mixed phenotype leukemia (excluding T-ALL with myeloid antigen expression)
- **3.2.2.** History of another primary invasive malignancy that has not been definitively treated and in remission. Patients with non-melanoma skin cancers or with carcinomas in situ are eligible regardless of the time from diagnosis (including concomitant diagnoses).
- **3.2.3.** Presence of clinically significant uncontrolled CNS pathology such as epilepsy, childhood seizure, paresis, aphasia, stroke, severe brain injuries, organic brain syndrome, or psychosis.
- **3.2.4.** Patients with a cardiac ejection fraction (as measured by either MUGA or echocardiogram) < 50% or with a history of absolute decrease in LVEF of  $\ge 15$  absolute percentage points are excluded.
- **3.2.5.** Medical history of cardiovascular disease such as:
  - **3.2.5.1.** Clinically significant cardiac disease including congestive heart failure (NYHA class III or IV), arrhythmia or conduction abnormality requiring medication, or cardiomyopathy
  - **3.2.5.2.** Clinically uncontrolled hypertension

Age	Blood Pressure
12 to 13	>120/80mmHg
>13	>140/90mmHg

- **3.2.5.3.** Complete left bundle branch block
- **3.2.5.4.** Right bundle branch block + left anterior hemiblock
- **3.2.5.5.** Congenital long QT syndrome

Page | 10 04/25/2024

- **3.2.5.6.** History or presence of sustained or symptomatic ventricular tachyarrhythmia, atrial fibrillation, or clinically significant resting bradycardia (< 50 bpm)
- **3.2.5.7.** Corrected QT interval using Fridericia formula (QTcF) > 450 ms for males and > 470 ms for females at the screening ECG
- **3.2.5.8.** QRS  $\geq$  110 ms
- **3.2.5.9.** History of symptomatic congestive heart failure
- **3.2.6.** Patients with uncontrolled, active infections (viral, bacterial, or fungal). Infections controlled on concurrent anti-microbial agents are acceptable. Anti-microbial prophylaxis per institutional guidelines is acceptable.
- **3.2.7.** Known active hepatitis B or C infection or known seropositivity for HIV.
- **3.2.8**. Liver cirrhosis or other active severe liver disease or suspected active alcohol abuse.
- **3.2.9.** Have conditions requiring chronic systemic (not inhaled) glucocorticoid use, such as autoimmune disease or severe asthma. Low doses of corticosteroids (10 mg prednisone equivalent a day) are permitted.
- **3.2.10.** Patients with unresolved nausea, vomiting, or diarrhea of CTCAE version 5.0, grade > 1 from prior therapy.
- **3.2.11.** Patients with impairment of GI function or GI disease presence that may significantly alter the absorption of CB-103 (e.g., ulcerative diseases, uncontrolled nausea, vomiting, diarrhea, malabsorption syndrome, or small bowel resection).
- **3.2.12.** Have current or recurrent (within 3 months) gastrointestinal disease, have conditions requiring chronic systemic glucocorticoid use, have active graft versus host disease, or have a second primary or prior malignancy that would affect the interpretation of study results. Low doses of corticosteroids (10 mg prednisone equivalent a day) are permitted.
- **3.2.13.** Prior chemotherapy/radiotherapy/investigational therapy within 2 weeks before the start of study drugs with the following exceptions:
  - **3.2.13.1.** Up to 5 days of glucocorticoids (10 mg of dexamethasone or equivalent/day) in combination with up to 3 doses of cyclophosphamide (200 mg/m $^2$ /day) are allowed as standard pre-phase treatment up to 1 day before start of study treatment. Cytarabine up to 2gm/m $^2$  are also allowed as standard pre-phase treatment up to 1 day before start of study treatment.
  - **3.2.13.2.** Mercaptopurine may be dosed up to 5 days prior to first dose of CB103
  - **3.2.13.3.** Vinca alkaloids may be dosed up to 5 days prior to first dose of CB103
  - **3.2.13.4.** Prophylactic intrathecal (IT) chemotherapy may be dosed up to 1 day prior to first dose of CB103
- **3.2.14.** Females who are pregnant or lactating.

Page | 11 04/25/2024

- **3.2.15.** Male or female subjects of childbearing potential, unwilling to use an approved, effective means of contraception in accordance with institution's standards.
- **3.2.16.** Other severe, uncontrolled acute or chronic medical or psychiatric condition or laboratory abnormality that in the opinion of the Investigator may increase the risk associated with study participation or investigational product administration or may interfere with the interpretation of study results and/or would make the patient inappropriate for enrollment into this study.
- **3.2.17.** Patients who are unable or unwilling to comply with all study requirements for clinical visits, examinations, tests, and procedures.
- **3.2.18.** Patients must be excluded if they are currently enrolled in another ongoing clinical trial with anti-cancer investigational products

#### 4. TREATMENT PLAN

# 4.1. Study Design

[figure not shown]
This study is designed as a phase II open-label single-arm clinical trial to evaluate the efficacy and safety of CB-103 in combination with venetoclax in adolescent and adult patients with T-ALL/T-LBL with relapsed or refractory disease.

Patients are eligible independently of Notch pathway activation in the leukemic blasts: however, a fresh marrow/blood sample must be obtained before starting the study treatment to classify the patients as being either Notch positive or negative. Notch pathway activation is defined presence of Notch1 gain-of-function (GOF) mutations, or FBXW7 loss-of-function (LOF) mutations, or Notch3 GOF mutations or Notch1 translocations detected by Next Generation Sequencing (NGS). Details on molecular alterations as signs of Notch pathway activation and the specific test method can be found in the laboratory manual.

The study consists of three periods (Figure 2):

- Screening period (including baseline assessments)
- Treatment period (including an End-of-Treatment [EOT] visit)
- Survival follow-up period

Figure 2: Study design schema

A cycle of treatment is defined as 28 days of treatment with CB-103 and Venetoclax.

Page | 12 04/25/2024

#### 4.2. Treatment Plan

#### 4.2.1. Induction cycle

All eligible patients will receive the 1st cycle (**induction cycle**; day 1-28) with CB-103 and venetoclax.

# 4.2.2. Reinduction cycle

Patients achieving benefits from the treatment – benefit is defined as achieving at least stabilization of the disease - are eligible to receive a 2nd cycle (**reinduction cycle**, day 29-56) of CB-103 and venetoclax at the same dose as in the induction cycle.

In patients who did not attain a defined clinical response after the induction cycle i.e. non responders, a reinduction cycle of CB-103 and Venetoclax may be administered if there was no unacceptable toxicity.

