# 4.3.1. End of 1st Cycle (induction cycle)

Patients are assessed for disease response on day 28 from the start of treatment (end of the **induction cycle**).

If the day 28 marrow is not hypocellular (cellularity  $\leq$  15%) and the patient is showing at least stabilization of the disease or a clinical benefit in the investigator's judgement, the patient may enter the **reinduction** cycle of CB-103 and venetoclax. Patients are defined to have a clinical benefit, if they are in complete remission (CR) or complete remission with incomplete blood count recovery (Cri), or have a decrease in disease burden, including peripheral blasts or bone marrow blasts that do not meet the criteria for CR or Cri, or have no evidence of progression.

If the day 28 marrow is hypocellular (cellularity  $\leq$  15%), then a repeat bone marrow biopsy is obtained between days 36 and 42 to assess response; if the repeat marrow is not hypocellular (cellularity  $\leq$  15%) and the patient is showing at least stabilization of the disease, the patient may enter the **reinduction** cycle of CB-103 and venetoclax.

Page | 13 04/25/2024

If the peripheral counts do not recover (ANC <  $1 \times 10^9$ /L or platelets count <  $60 \times 10^9$ /L) and there is evidence of residual leukemia in the bone marrow, the patient may enter the **reinduction** cycle of CB-103 and venetoclax at the discretion of the treating physician, after a minimum of 4 weeks from the start of the last cycle.

Patients who do not attain a defined clinical response after the **induction** cycle, may enter the **reinduction** cycle of CB-103 and venetoclax if there was no unacceptable toxicity.

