# 4.3.2. End of 2nd Cycle (reinduction cycle)

Patients are assessed for disease response on day 56 from the start of treatment (end of the **reinduction cycle**):

- 1. If the day 56 marrow is not hypocellular (cellularity ≤ 15%) and the patient is showing a CR or a CRi, the patient is eligible for **maintenance** with CB-103 and venetoclax until disease progression or bone marrow transplant in the absence of discontinuation criteria.
- 2. If the day 56 marrow is hypocellular (cellularity ≤ 15%), then a repeat bone marrow biopsy is obtained between days 66 and 70 to assess response; if the repeat marrow is not hypocellular (cellularity ≤ 15%) and the patient is showing a CR or a CRi, the patient is eligible for maintenance with CB-103 and venetoclax until disease progression or bone marrow transplant in the absence of discontinuation criteria.
- 3. Patients with PR or stable disease (SD) after the reinduction cycle may continue the treatment with the combination of CB-103 and venetoclax for a maximum of three additional cycles or until disease progression or bone marrow transplantation, whicher comes first.
- 4. Non-responding patients, i.e patients without Cr or Cri or PR or SD after the reinduction cycle are discontinued from the treatment.

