#### 4.3.3. End of Treatment

Treatment will continue until discontinuation due to unacceptable toxicity, lack of response, relapse or progressive disease. This includes any of the following:

- 1. Clinically significant progressive disease at any time.
- 2. Death
- 3. Possibility of undergoing allogeneic stem cell transplantation.
- 4. Intercurrent illness that prevents further administration of treatment.
- 5. Unacceptable adverse event(s), that are not manageable with dose adjustments and/or optimal medical management, or that, in the opinion of the Investigator, pose an unacceptable risk for the patient.
- 6. Patient decision for study withdrawal.

General or specific changes in the patient's condition that render the patient unacceptable for further treatment in the judgment of the Investigator, sponsor, or any regulatory body.

End of Treatment (EoT) visit is to be done 5 days after the last dose of any study treatment, unless the patient starts any subsequent antitumor therapy (in which case the EoT visit should be performed before the start of the new therapy, whenever possible).

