#### 11. TREATMENT DISCONTINUATION

Treatment will continue until discontinuation due to unacceptable toxicity, lack of response, relapse or progressive disease. This includes any of the following:

- Clinically significant progressive disease at any time.
- Death
- Possibility of undergoing allogeneic stem cell transplantation.
- Intercurrent illness that prevents further administration of treatment.
- Unacceptable adverse event(s), that are not manageable with dose adjustments and/or optimal medical management, or that, in the opinion of the Investigator, pose an unacceptable risk for the patient.
- Patient decision for study withdrawal.
- General or specific changes in the patient's condition that render the patient unacceptable for further treatment in the judgment of the Investigator, sponsor, or any regulatory body.

Page | 48 04/25/2024

Patients who discontinue treatment due to unacceptable toxicity, lack of response, relapse or progressive disease, or bone marrow transplantation are considered to have completed the study treatment per protocol. The patients need to complete End Of Treatment (EOT) visit.

Once a patient has discontinued the study treatment and has completed the EOT visit, the patient shall be followed-up for survival up to two years from enrollment onto the study: data on survival status and any new anti-cancer therapy may be collected by phone every 3 months for up to 2 years after study enrollment. In case of relevant related toxicities (i.e., Grade>1) occurring during survival follow-up, the relevant information will be collected every 4 weeks until resolution or stabilization of the event: information collected bytelephone contact is acceptable.

At disease progression or treatment discontinuation, the emergence of new neoplastic clones or further mutations during therapy with this combination shall be investigated by next generation sequencing (NGS) in peripheral blood mononuclear cells (PMBC) or, If available, bone marrow samples obtained from patients.

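### Sections 4.2.2 and 4.3.1 allow reinduction in patients who have progressed by day 28, sections 4.3.3, 5.1.3 and 11 end treatment at progression, and nothing says which prevails

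*Combined protocol and SAP*

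**What the plan says.** **Texts that permit a second cycle.** Section 4.2.2 first offers reinduction to patients who benefit, where "benefit is defined as achieving at least stabilization of the disease". A second paragraph then covers patients without a defined clinical response after induction, "i.e. non responders, a reinduction cycle of CB-103 and Venetoclax may be administered if there was no unacceptable toxicity". Section 4.3.1 has the same structure. Its definition of clinical benefit already takes in patients who are in remission, have a reduced disease burden, "or have no evidence of progression". Its closing paragraph, which begins "Patients who do not attain a defined clinical response after the" induction cycle, lets those patients into reinduction on the single condition that toxicity was not unacceptable.

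**Texts that end treatment.** Sections 4.3.3 and 11 open with the same sentence: "Treatment will continue until discontinuation due to unacceptable toxicity, lack of response, relapse or progressive disease". The first item in both lists is "Clinically significant progressive disease at any time". Section 5.1.3 gives CB-103 until the investigator judges that the disease has progressed, alongside limits for toxicity and continuing benefit.

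**Text on non-response after cycle 2.** Section 4.3.2, item 4: "Non-responding patients, i.e patients without Cr or Cri or PR or SD after the reinduction cycle are discontinued from the treatment".

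**Endpoint texts.** Section 12 reads ORR (CR, CRi or PR) after the first two cycles. Section 4.3 does not replace patients removed in cycle 1 for toxicity or progression. For EFS, section 9.1.5 names treatment failure, relapse from CR and death, whichever is first. Progression enters the EFS rule only through the censoring sentence.

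**The concern.** A patient found to have progressed at day 28, without unacceptable toxicity, meets a text that permits cycle 2 and a text that ends treatment. The choice falls to the treating physician in an open-label, single-arm trial, and two like patients can be handled in opposite ways.

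The choice decides who can still become a responder. A patient treated on has a day-56 assessment, and nothing in sections 9 or 12 fixes day-28 progression as non-response. A stopped patient is not replaced and has no cycle 2 assessment: footnote 18 of Table 16 continues tumour assessment only for those who stopped without progression. The choice also decides how much treatment a progressing patient receives.

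EFS is affected more narrowly. Treatment failure is not defined, so a reinduced progressor may or may not be given an event at day 28.

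**Working it through.** **1. Whom the second permission reaches.**

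| Status at day 28 | Text permitting cycle 2 | Text ending treatment |
|---|---|---|
| CR, CRi, PR or stable disease | First permission in 4.2.2; clinical benefit in 4.3.1 | None for progression |
| Progression, not called clinically significant | Second permission in 4.2.2; last paragraph of 4.3.1 | Opening sentence of 4.3.3 and 11; 5.1.3 |
| Clinically significant progression | Same | Same, plus the first item of 4.3.3 and 11, which applies at any time |

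If non-responder has the meaning in 4.3.2 item 4 (no CR, CRi, PR or SD), the second permission is for progressors. If it means no response of the kinds defined in 9.1.2 (CR, CRi, PR), it covers stable disease again and still includes progressors. On both readings, rows two and three carry opposing texts with no order of precedence.

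**2. The plan's own figures.** The Beta marginals of the Dir(0.05, 0.1, 0.15, 0.7) prior are Beta(0.15, 0.85) for response and Beta(0.2, 0.8) for toxicity. With λ = 0.57 and α = 0.86 (α/3 for toxicity), the stopping limits at 10, 20 and 30 patients come out as responses ≤ 0, 2, 5 or toxicities ≥ 3, 5, 6, which is Table 18. Exact enumeration with these limits gives a probability of claiming the treatment acceptable of:

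- 78.46% at p_eff 0.30, p_tox 0.10 (Table 19: 77.76%)
- 8.17% at p_eff 0.15, p_tox 0.20 (Table 19: 8.34%)

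The second difference is 0.17 points, against a simulation standard error of √(0.0834 × 0.9166 / 10000) = 0.28 points. All ten scenarios agree within 0.8 points, so the design arithmetic is sound. At 30 patients one response separates the outcomes: 5 is unacceptable, and 6 is acceptable if toxicities are below 6.

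**3. Possible size.** The documents give neither the number progressing at day 28 nor their chance of responding in cycle 2. Assume 6 to 12 of 30 progress and 5% to 8% of them would respond if treated on.

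- Extra responses: 6 × 0.05 = 0.30, up to 12 × 0.08 = 0.96
- Shift in ORR: 0.30 / 30 = 0.010, up to 0.96 / 30 = 0.032

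If ORR is 0.15 when progressors are stopped, it becomes about 0.16 to 0.18 when they are treated on. The probability of claiming acceptable (response with toxicity 0.05) is then:

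| Two-cycle ORR | p_tox 0.20 | p_tox 0.10 |
|---|---|---|
| 0.15 | 8.17% | 21.03% |
| 0.16 | 10.21% | not run |
| 0.17 | 12.37% | 30.52% |
| 0.18 | 14.59% | 35.47% |

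In the other direction, if 0.30 is reached only when progressors are treated on, stopping them and losing 0.02 lowers power at p_tox 0.10 from 78.46% to 74.41%.

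As an outer bound, take a shift of 0.10, or 3 responses in 30. At p_tox 0.10 the figures become 65.94% (from 21.03%) and 45.28% (from 78.46%). If progressors almost never respond late, the effect on ORR is close to nil.

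**The case against.** **The texts can be read together.** The permission says may, and the listed stop is for clinically significant progression. A non-responder could have cycle 2 unless progression is clinically significant. This reading is available but unstated. The opening sentence of 4.3.3 and 11 and the progression limit in 5.1.3 lack the qualifier, and clinically significant is not defined for day 28. Section 5.1.3 also mentions continuing benefit and refers back to section 4.2, so it does not settle the matter.

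**Lack of response is not a conflict.** A reader might infer that every cycle 1 non-responder meets a stop in 4.3.3 and 11. Section 4.3.2 item 4 can be read as timing that stop after reinduction, and the permissions in 4.2.2 and 4.3.1 fit this. The objection largely stands. The conflict rests on progression.

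**Day-28 progressor is not a defined category in marrow disease.** Section 9.1.2 defines relapse after CR but not progressive disease; Appendix 2 defines it for extramedullary disease. This is true, but it widens the room for judgement.

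**EFS already takes the first event.** A reader might infer that EFS and ORR contradict each other when progression at day 28 is followed by response at day 56. They do not: two endpoints may classify one patient differently. The gap is only that treatment failure is not said to include progression.

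**The effect is small and the criteria are non-binding.** Both are fair, and both limit the weight of the point.

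**Conclusion.** The conflict over progression at day 28 is real. It bears on treatment exposure and on who can reach the two-cycle ORR, and the text does not resolve it. The lack-of-response wording is a weaker conflict and would not carry the point alone.

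The size cannot be found from the documents. Under the assumed 6 to 12 progressors and 5% to 8% late response, it is under one response in 30.

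Two stronger conclusions are tempting and unsupported. First, a reader might take the rise from 8.2% to 10.2% or 14.6% as type I error inflation. The later figures are acceptance probabilities at a two-cycle ORR of 0.16 and 0.18. A genuine CR, CRi or PR at day 56 is a response under the endpoint as defined, so they are not error rates at a true 0.15. Second, a reader might say that patients would be treated past a stopping rule. That presumes the stop prevails, which is exactly what the documents leave open.

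**What to change.** 1. Reconcile 4.2.2 and 4.3.1 with 4.3.3, 5.1.3 and 11 so that one rule covers a patient with progression at day 28. Which rule applies is for the sponsor and the investigator; this review takes no position.
2. Whichever rule is kept, state in 9.1.5 that documented progression counts as treatment failure for EFS and is dated when first documented, even if treatment continues.
3. Optionally, list any ORR responder who had progression at day 28, so that readers can see how far the rule affected the primary count.

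The cost is amendment wording and one analysis sentence. Sample size, boundaries and visit schedule need not change on this account.
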